5.7 Premature termination of the study

Because the devices used in this study are CE marked and will be used according to its labeling, there are no preconceived reasons for premature termination of the study. Upon the sponsor / principal investigator's decision to terminate or suspend the study, the involved parties and METC will be notified promptly, stating the reasons.

6. SAFETY REPORTING

6.1 Temporary halt for reasons of subject safety

In accordance to section 10, subsection 4, of the WMO, the sponsor as represented by the principal investigator will suspend the study if there is sufficient ground that continuation of the study will jeopardise subject health or safety. The principal investigator will notify the accredited METC without undue delay of a temporary halt including the reason for such an action. The study will be suspended pending a further positive decision by the accredited METC. The investigator will take care that all subjects are kept informed.

6.2 AEs, SAEs and SUSARs

6.2.1 Adverse events (AEs)

Adverse events are defined as any undesirable experience occurring to a subject during the study, whether or not considered related to the implants. Only relevant adverse events reported spontaneously by the subject or observed by the investigator

or his staff will be recorded. The following AE's are directly related to the surgical procedure, and will therefore not be recorded by the investigator: nausea, headache, pain, haemorrhage and wound leakage

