Most dislocations occur during the first year after surgery, of which approximately half within the first three months after operation.²⁻⁵ Hip dislocation is a major problem that results in reduced functioning and a deterioration in quality of life⁶, especially in patients with recurrent dislocation who often need revision surgery. In order to establish value based health care for patients with hip osteoarthritis, hospitals within the Santeon network asked patients which outcomes are of value to them. The patients indicated that they feared hip dislocation and that its prevention is paramount to them [personal communication]. In addition to the negative consequences of dislocation for the patients, dislocations also increase healthcare costs.^{7;8} A single dislocation was estimated to add 19% to the hospital costs of an uncomplicated THA, and a revision surgery up to 148%.8 With an average cost for a primary THA of about €10.000 in the Netherlands, this implies additional costs after dislocation that range from €1.900 to €15.000 per case. To address the problem of dislocation, the dualmobility (DM) cup was developed in France in the 1970's. 10 The DM cup consists of two articulations between three different components; a metallic acetabular shell, a mobile polyethylene liner and a femoral head. The mobile polyethylene liner articulates both with the acetabular shell and the femoral head. This should provide more stability and biomechanically reduce the risk of dislocation. 11-14 Dislocation rates reported for the DM-cup range from 0 to 4.6%12;14-18 which seems slightly lower than the 0.5 to 6% reported for unipolar cups. 19-24 Also, the use of DM cups for revision surgery in patients with recurrent dislocation has shown promising results.^{2;25;26} The Dutch national arthroplasty registry (LROI) shows that in 2015 3.9% of all cemented cups was a DM cup.²⁷ These DM cups are mainly used in patients with specific characteristics, such as cognitive impairment (not able to follow restrictions after surgery) or neuromuscular diseases (spasms) or as a standard procedure for revision surgeries due to recurrent dislocations. Internationally, DM cups are used more widespread. For instance, in France DM cups are used in an estimated 30% of all THAs.²⁸ Potential disadvantages of DM cups are loosening, intra prosthetic dislocation and psoas impingement.^{29;30} In the Netherlands, most DM cups are placed because of specific patient characteristics.³¹ These characteristics might negatively affect the risk for dislocation and revision surgery compared to the general THA population. Nevertheless, several studies reported similar failure rates between DM and unipolar cups. 12;14;17;32

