2. STUDY DESIGN

Design

A prospective multi centre single blinded randomised controlled trial, nested in the national

Version number: 7.0.,14-11-2023 9 of 26

registry of orthopaedic implants to compare the number of hip dislocations following primary total hip arthroplasty (THA), using the posterolateral approach, with a dual-mobility (DM) cup compared to a unipolar cup.

All patients will be followed-up until 2 years after surgery, and after final study follow up, participants remain traceable in the national joint registry for evaluation of long-term survival and mortality.

A third arm (non-randomised) consists of patients that are not eligible for a unipolar cup and therefore will receive a dual mobility cup. See figure 1 for an overview.

[figure not shown]

Figure 1. Flowchart with the 3 study groups.

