5.3 Study procedures

During the pre-operative visit at the outpatient clinic, patients who are potential candidates for this study will be screened to determine if they meet the inclusion / exclusion criteria. If the patient is eligible, the investigator (or his designated representative) informs the patient about the study and proposes study participation, according to GCP guidelines. If desired, an additional telephone appointment can be arranged. Patients must sign an ethical committee (METC) approved study informed consent form (ICF) prior to participating in any study specific activities. The ICF can be signed face to face by the patient and investigator, or the patient can sign the ICF remotely and send it to the investigator by mail (due to COVID-19 restrictions). Subsequently, the investigator can sign the ICF and send one version to the patient. The ICF will be stored in a locked closet in the participating center. Pre-operative data will be collected including: demographics and medical history, NRS for pain in rest and during weight bearing, HOOS-PS and EQ-5D. The patients are also asked to fill out questionnaires. See table 1 for an overview of all measurements and follow-up moments.

Evaluation moment	Pre-operative	Intra-operative	3 months	1 year	2 years
Preoperative data (screening)	х				
Surgical Details		х			
PROMs	х		х	х	х
Serious Adverse Events	Anytime				

Table 1: Overview of follow-up moments.

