6.2.2 Serious adverse events (SAEs)

A serious adverse event is any untoward medical occurrence or effect that

- results in death;
- is life threatening (at the time of the event);
- requires hospitalisation or prolongation of existing inpatients' hospitalisation;
- results in persistent or significant disability or incapacity;
- is a congenital anomaly or birth defect; or

(S)AEs that are related to a previous known or unknown disease, or conditions that cannot be related to the procedure (like accidents or related to other interventions) will not be recorded. An elective hospital admission will not be considered as a serious adverse event.

The investigator will report the potentially study-related SAEs, as defined above, through the web portal *ToetsingOnline* to the accredited METC that approved the protocol, within 7 days of first knowledge of the investigator for SAEs that result in death or are life threatening followed by a period of maximum of 8 days to complete the initial preliminary report. All other SAEs will be reported within a period of maximum 15 days after the investigator has first knowledge of the serious adverse events.

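### The rule in 6.2.1 that five symptoms are not recorded as adverse events has no time window, and the protocol does not say whether it yields to the SAE rules in 6.2.2

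*Protocol*

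**What the plan says.** Section 6.2.1 opens with a wide definition: "Adverse events are defined as any undesirable experience occurring to a subject during the study, whether or not considered related to the implants". It then narrows what is written down to relevant events that the patient volunteers or that staff notice. Finally it removes five terms outright. The reason is "The following AE's are directly related to the surgical procedure", and the consequence is that they "will therefore not be recorded by the investigator: nausea, headache, pain, haemorrhage and wound leakage". No onset limit, severity threshold or exception for serious events is attached.

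Section 6.2.2 defines SAEs on their own terms. One criterion is that the event "requires hospitalisation or prolongation of existing inpatients' hospitalisation". It has its own exclusion, for earlier disease and for conditions that cannot be attributed to the procedure, and does not repeat the five terms.

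On duration, section 2 states: "All patients will be followed-up until 2 years after surgery". Table 1 in section 5.3 has a row for "Serious Adverse Events" marked as collected at any time, and section 6.4 has SAEs reported until the end of the study.

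Under section 7.4, the interim review looks at revisions and SAEs by group without a formal test, and an excess may lead to early termination. Section 6.5 says there is no DSMB.

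**The concern.** The reason for the exclusion and its scope do not match. Pain, bleeding or a leaking wound in the first days can reasonably be put down to the operation. The same symptom at 12 or 18 months cannot simply be assumed to come from it, yet the rule treats both alike. The introduction says: "Potential disadvantages of DM cups are loosening, intra prosthetic dislocation and psoas impingement". Pain may be how loosening or impingement shows itself. That is a clinical inference and is not stated in the protocol, but it is an ordinary one.

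There is a second difficulty at the serious end. A haemorrhage or wound leak that prolongs the admission satisfies 6.2.2 and also carries a term on the 6.2.1 list. A site coordinator with both sections open finds no sentence saying which one governs. Two consequences follow: non-serious late events may be missing from the adverse event record, and SAE counts may depend on how each centre reads the text. SAE counts are one of the two safety quantities named for the interim review.

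**Working it through.** The protocol states no figure on this point, so there is nothing to reproduce. The check sets the sections side by side.

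**1. Is the exclusion limited in time or seriousness?** No. Section 6.2.1 gives the terms, the reason and the instruction, and nothing else. The exclusion therefore runs for the whole follow-up. For the randomised arms that is 550 + 550 = 1100 patients for up to 2 years each, or at most 1100 × 2 = 2200 patient-years before deaths and withdrawals.

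**2. What happens to a non-serious event after the perioperative period?**

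| Event | Adverse event record (6.2.1) | Other capture in the protocol |
|---|---|---|
| Late pain in the operated hip | Not recorded if the rule is read literally | NRS at rest and on weight bearing before surgery and at 3 months, 1 year and 2 years (5.1.2, Table 1) |
| Cup failure behind the pain | Loosening, impingement and intraprosthetic dislocation are not on the list, so they stay recordable under those names | Any revision (5.1.2); reoperations and complications of the device (7.2) |
| Late bleeding or wound leakage | Not recorded if the rule is read literally | None clearly stated, unless it leads to reoperation |

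The clearest gap is the last row. For pain, the loss is confined to the adverse event record.

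**3. What happens to a serious event with one of the five terms?** Take a wound leak that prolongs the index stay.

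- Under 6.2.2 it meets the hospitalisation criterion. It is related to the procedure, so the exclusion in that section does not remove it. It counts.
- Under 6.2.1 it is an undesirable experience during the study, so it falls within the definition, and its term is on the list. It is not recorded.
- No sentence ranks the two. The 6.2.2 exclusion is worded to cover both serious and non-serious events, so the rules of the two sections are not kept strictly apart. That leaves some room to think the 6.2.1 list reaches SAEs as well.

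**4. Where would inconsistent reading show?** In the SAE counts by group at the interim review, which takes place when 200 patients have reached the 3-month assessment. Randomisation is stratified by centre in small blocks (5.2). A centre that applies one reading to all its patients therefore affects both arms about equally: the counts become lower and less comparable between centres, but the arms are not systematically biased. A difference between arms would need the reading to vary with the implant. That cannot be excluded, because only patients are described as blinded, but nothing in the protocol shows it.

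**5. Can the effect be sized?** No. The protocol gives no expected rate for any of the five terms, early or late, so any number of missed events would be invented.

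**The case against.** The strongest reply is that the list sits under the heading for adverse events and speaks only of AEs, while SAEs have a free-standing definition, their own exclusion and their own collection rule up to the end of the study. On that reading a serious bleed is plainly an SAE. This is the more natural reading, and it is why a reader who infers that serious bleeding or wound events are lost goes further than the documents allow. What remains is an ambiguity, because the protocol does not say that 6.2.2 prevails.

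A second reply is that the exclusion carries its own limit: if the events are left out because they come from the operation, pain from a loose cup at 12 months falls outside the reason. That is a fair reading of intent, but the instruction is attached to the terms, and a centre following it as written would not record them.

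Third, the protocol names no comparison of non-serious adverse events between arms, and Table 1 schedules only SAEs. This stands and limits the stakes for late non-serious events.

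Fourth, a wide definition followed by a narrower recording rule is not in itself a contradiction. This also stands. The defect is the open-ended scope of the exclusion and the missing link to 6.2.2.

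**Conclusion.** The point holds in limited form. The exclusion in 6.2.1 is drawn too widely for its stated reason. Followed as written, it keeps late non-serious bleeding, wound leakage and operated-hip pain out of the adverse event record for up to 2 years. For events that meet a 6.2.2 criterion, the two sections leave it open which instruction applies, so centres may count SAEs differently in a review that can end the trial early and has no DSMB.

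A reader might also infer that the harms named for dual mobility cups are hidden from the trial. The documents do not support that: those diagnoses are not on the list, pain is measured to 2 years, and revisions, reoperations and device complications are to be analysed.

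The size is modest and cannot be put into figures from the protocol. The conclusion rests on two assumptions: that sites follow 6.2.1 literally, and that no other trial document, such as case report form instructions, already settles the matter.

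**What to change.** Reconcile 6.2.1 with 6.2.2 in a short amendment that says three things:

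- The five terms are left out of adverse event recording only when the event is non-serious and begins within a perioperative window, which the sponsor chooses and states.
- Any event that meets a criterion in 6.2.2 is recorded and reported as an SAE, whatever its term, subject only to the exclusions in 6.2.2 itself.
- After the window, the five terms follow the ordinary rule already in 6.2.1: relevant events that the patient volunteers or that staff observe.

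Sites need not be required to assign a cause to late pain. That could call for clinical assessment that Table 1 does not schedule, and the point does not depend on it.

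The cost is the amendment text, a note to centres and a small number of extra adverse event entries. No visit, questionnaire or procedure is added, and treatment is unchanged.

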6.2.2 Serious adverse events (SAEs)

A serious adverse event is any untoward medical occurrence or effect that

- results in death;
- is life threatening (at the time of the event);
- requires hospitalisation or prolongation of existing inpatients' hospitalisation;
- results in persistent or significant disability or incapacity;
- is a congenital anomaly or birth defect; or

(S)AEs that are related to a previous known or unknown disease, or conditions that cannot be related to the procedure (like accidents or related to other interventions) will not be recorded. An elective hospital admission will not be considered as a serious adverse event.

The investigator will report the potentially study-related SAEs, as defined above, through the web portal *ToetsingOnline* to the accredited METC that approved the protocol, within 7 days of first knowledge of the investigator for SAEs that result in death or are life threatening followed by a period of maximum of 8 days to complete the initial preliminary report. All other SAEs will be reported within a period of maximum 15 days after the investigator has first knowledge of the serious adverse events.

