5.1.2 Secondary study parameters/endpoints (if applicable)

- Revision surgery of any component for any reason
- Patient Reported Outcome Measures (PROMs)
 The following PROMs are already collected in the LROI according to follow-up of the Dutch orthopaedic association (NOV). This standard follow-up occurs pre- operative, 3 months and 1 year postoperative. For this study one extra measurement will be done at 2 years postoperative.
 - Physical functioning of the hip, measured by:
 - Hip disability and Osteoarthritis Outcome Score Physical Short form (HOOS-PS)⁴⁸
 - Quality of life, measured by:
 - EuroQol 5 Dimensions (EQ-5D)⁴⁹
 - o Pain, measured by:
 - Numeric Rating Scale (NRS) for pain in rest rest and during weight bearing
 - Change in functioning, measured by:
 - An anchor question about change in functioning.

Added as extra question to the standard PROMs:

- Fear of hip dislocation on a 5 point Likert scale
 - Added at all follow-up moments
- Healthcare and societal costs related to hip dislocation or surgery.
 - Added at 3 months and 1 year postoperative.
- Education level

 Added as extra question to the PROMs at baseline: "What is the highest education level you achieved?" Answer options according to CBS classification.

- Awareness of type of cup that was placed
 - Added as extra question to the PROMs at all follow-up moments: "Do you know what type of cup was placed?", "If yes, how did you get this information?"
- Long term (5and 10year) implant survival and mortality based on national registry data.

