7. STATISTICAL ANALYSIS

7.1 Primary study parameter(s)

The primary outcome, the difference in number of dislocations in both groups, will be analysed using the chi-square test. In case the assumptions of this test are not met, Fischer exact test will be applied. Multilevel logistic regression analysis will be used for analyses in which we adjust for clustering of data (e.g. at the hospital level), possible confounding and effect modification. A multilevel survival model will be used to analyse the survival of the implant, corrected for covariates.

The best way to handle missing values will be defined and applied for all analyses, including the cost-effectiveness analysis.

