10. STRUCTURED RISK ANALYSIS

There is minimal risk associated with participating in this study over and above that of the primary hip arthroplasty procedure. Serious complications may be associated with any total joint replacement surgery. These complications include, but are not limited to: infection; genitourinary disorders; gastrointestinal disorders; vascular disorders, including thrombus; bronchopulmonary disorders, including emboli; myocardial infarction or death.

All devices are CE marked and will be used according to its labelling. Patients will be treated in the best medical judgment of the surgeon, regardless of the study protocol. Assessment involves questionnaires and anterior-posterior and lateral radiographs. The patient's burden from the study consists of extra questions added to questionnaires at the standard LROI follow-up moments (5 minutes extra at 3 months and 1 year) and one extra questionnaire at 2 year follow-up (15 minutes extra).

In addition to the benefits from the primary hip arthroplasty procedure e.g. reduced pain, improved range of motion, patients might benefit from the type of acetabular cup that is used in this study. Patients in the intervention group receive a dual mobility cup, instead of a unipolar acetabular cup. Dual mobility cups are designed to reduce the risk of hip dislocation.

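### The SAE recording rule in section 6.2.2 leaves out events attributed to prior disease, with no exception for death, so the SAE counts by arm weighed at the interim depend on an attribution open to knowledge of allocation

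*Protocol*

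**What the plan says.** Section 6.2.2 opens its definition with "A serious adverse event is any untoward medical occurrence or effect that" and puts death first in the list of qualifying outcomes. Below the list comes the recording rule. It covers "S)AEs that are related to a previous known or unknown disease, or conditions that cannot be related to the procedure" and closes with "like accidents or related to other interventions) will not be recorded". Death is not exempted. The same section then limits expedited reporting to the ethics committee to potentially study-related SAEs, and names the investigator as the person who reports.

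Section 6.2.1 defines adverse events on a different principle: they count "whether or not considered related to the implants".

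Section 5.2 blinds the patients only, and the investigator or a representative performs the randomisation. Section 7.4 has the number of SAEs in each group considered at the interim analysis without a formal test, and names early termination as a possible response to more SAEs. Section 6.5 states that there will be no DSMB.

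Mortality appears among the endpoints in section 5.1.2 as "Long term (5and 10year) implant survival and mortality based on national registry data". The objectives in section 1 likewise tie it to 5 and 10 years.

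**The concern.** The rule governs whether an event is recorded at all, not how fast it is reported. An event judged to stem from a prior disease leaves no trace in the trial's safety data, and nobody can later review that judgement. Attribution to an unknown disease cannot be checked even in principle. In patients aged 70 or over, there will often be a prior disease to which a death or serious event can be assigned.

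The SAE counts by arm are therefore counts after a judgement. If that judgement is made with knowledge of the cup, it can differ between arms. These counts are one of three things weighed at the interim, beside dislocations and revisions. A statistical analysis plan cannot repair this, because it cannot restore events that the protocol says not to record.

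**Working it through.** The plan states no mortality or SAE rate, so there is no figure of its own to reproduce. The check is mainly a reading of the text, with a range for scale.

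**Following one event through the text**

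1. A patient dies at month 6 and the death is put down to a prior disease. By the definition in 6.2.2 this is an SAE.
2. By the next rule in 6.2.2 it is not recorded.
3. The protocol does not say who makes the attribution. 6.2.2 names the investigator as reporter, and 5.2 has the investigator or a representative randomise. Nothing requires the attribution to be made blind to allocation.
4. Mortality is named again only for the 5- and 10-year registry analyses. Section 2 describes registry traceability as applying after the final study follow-up. The Summary says that the Dutch registry holds mortality data, but no section commits to using them at 1 or 2 years.
5. A non-fatal SAE put down to a prior disease is also not recorded, and the protocol does not say that the registry would supply it.

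**How many deaths are subject to the rule**

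Inputs: 550 patients per arm (3.4). Annual mortality m of 1% to 5% is an assumption; the protocol gives none.

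- By 1 year, per arm: 550 × m = 550 × 0.01 = 5.5 to 550 × 0.05 = 27.5.
- By 2 years, per arm: 550 × [1 − (1 − m)²] = 550 × 0.0199 = 10.9 to 550 × 0.0975 = 53.6.
- At the interim, when 200 patients have reached 3 months (7.4), with deaths spread evenly over the year: 200 × m × 0.25 = 0.5 to 2.5 deaths in both arms together over those 3 months.

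These are all deaths, not unrecorded deaths. Deaths judged related to the procedure stay in, and the split is unknown. At the interim the expected number is so small that leaving out one or two deaths could change how the arms compare.

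**Effect on QALYs if deaths were handled as living non-responders**

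This handling is hypothetical. Assume utility u of 0.75 to 0.85 and deaths spread evenly over the year.

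- Overstatement of each arm's mean at 1 year: u × m / 2 = 0.75 × 0.01 / 2 = 0.00375 to 0.85 × 0.05 / 2 = 0.02125.
- Error in the difference between arms: u × d / 2, where d is the difference in mortality. It is 0 when d = 0, and 0.00375 to 0.00425 when d is 1 percentage point.

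The error in each arm cancels in the comparison unless mortality differs by cup type, and the documents give no figure for such a difference.

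**The case against.** The best defence is proportionality. The devices are CE marked and used as labelled, section 6.5 deems the added risk negligible, and limiting safety capture to events that could be related to the procedure is a common choice in such trials. The interim SAE counts are not tested, and the results go to the steering committee, the funding foundation and the ethics committee. The trial is also nested in a registry that holds mortality data, so deaths may be retrievable.

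Part of this stands. Limiting what is reported urgently is reasonable, and 6.2.2 already does so through its own reporting sentence, so the recording exclusion is not needed for that purpose. Registry data may well recover dates of death, but the protocol does not commit to that at 1 and 2 years.

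A reader might infer four stronger things that the documents do not support:

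- **Deaths will be treated as missing data.** Section 7.1 says only "The best way to handle missing values will be defined and applied for all analyses, including the cost-effectiveness analysis". It never classes death as missing. Setting utility to zero after death is detail that an analysis plan or health-economic plan normally carries.
- **QALYs will be distorted by as much as the treatment effect.** The error in each arm cancels if mortality is equal. Chance imbalance in deaths is ordinary sampling variation, which a correct analysis would contain as well.
- **The rule contradicts section 10.** That section lists "bronchopulmonary disorders, including emboli; myocardial infarction or death" among complications that joint replacement surgery may bring. Events of that kind that can be related to the procedure remain recordable, so the two sections are compatible.
- **The surgeon makes the attribution.** The text does not say so.

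**Conclusion.** The point holds as one about safety data capture. As written, section 6.2.2 keeps some deaths and other serious events out of the record on a judgement of relatedness that has no clear limit and need not be blind. Section 7.4 then uses the resulting counts by arm, without a DSMB. The tension with the definition in 6.2.1 supports this reading. It is not a flat contradiction, because 6.2.1 speaks of relation to the implants and 6.2.2 of relation to the procedure.

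The size cannot be fixed from the documents. On the assumed mortality range, some 5 to 28 deaths per arm by 1 year and 11 to 54 by 2 years are subject to the rule, of which an unknown share would go unrecorded. No bias in dislocation, revision or QALY results is shown. The amendment is worth making because the gap is plain in the text and cheap to close.

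**What to change.** Amend section 6.2.2 as follows:

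- Exempt death from the non-recording rule.
- Record date and cause of every death through 2 years whatever its attribution, or state that registry deaths will be used at 1 and 2 years. If the registry route is chosen, confirm that it covers every participating country, since the inclusion criteria admit Dutch, Spanish and Swedish speakers.
- Delete the reference to unknown disease.
- Use relatedness only as the filter for expedited reporting to the ethics committee, so that SAE counts compared by arm, including those at the interim, do not depend on an attribution made with knowledge of allocation.

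The cost is a wording amendment and some additional event records: on the assumed range, at most about 22 to 107 deaths over 2 years in 1100 patients (1100 × 0.0199 to 1100 × 0.0975), plus the non-fatal SAEs now left out. Expedited reporting need not grow, because 6.2.2 already restricts it to potentially study-related events.
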